**10.0 Patient Assessment**

**10.1 Study Parameters**

The following are suggested patient follow-up intervals and evaluations that may be performed to either assess for treatment toxicity or tumor response to SBRT:

Assessment	Pre-Rx	Post-Rx 6 wk	Post-Rx 3 mo	Post-Rx 6 mo	Post-Rx 9 mo	Post-Rx 1 yr
H&P / Weight	X	X	X	X	X	X b
Disease status	X	X	X	X	X	X b
AUA/EPIC Questionnaire	X	X	X	X	X	X
Toxicity Assessment		X	X	X	X	X b
PSA	X	X	X	X	X	X

AST/ ALT / Alk Phos	X a					
Total Bilirubin	X a					
PT/ PTT	X a					
Creatinine	X a					
CBC with Platelets	X					
Bone scan	X a					
CT/MR abdomen/pelvis	X					X b

- a. if clinically appropriate  
b. at the discretion of the treating radiation oncologist

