## **2.0 Objectives**

This study will evaluate the local control rate as well as acute and late toxicity rates of stereotactic body radiotherapy (SBRT) for the treatment of organ confined prostate cancer.

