### **2.3 End Points**

- 2.3.1 Primary endpoints will be biochemical control rate
  - Serial blood tests for prostate specific antigen (PSA) levels will be obtained at regular intervals
  - The "Phoenix definition" for biochemical recurrence (nadir + 2 ng/ml) will be used
- 2.3.2 Secondary endpoint will be late toxicity rate.
  - Grading of acute and late complications is defined in Section 12.3 (Appendix III)

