#### **5.0 Fiducial Placement**

- 5.1 Three gold fiducials will be placed within the prostate gland under ultrasound guidance in different locations
- 5.2 Fiducials should be placed at least 7 days prior to simulation because of the possibility of migration

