**13.4 Appendix IV ON-STUDY AUA SYMPTOM SCORE**

PLEASE FILL OUT THIS SHORT QUESTIONNAIRE TO HELP US FIND OUT MORE ABOUT ANY URINARY PROBLEMS YOU MIGHT HAVE. CIRCLE A NUMBER IN EACH COLUMN THAT BEST DESCRIBES YOUR SITUATION. YOU MUST ANSWER ALL QUESTIONS.

	Not at all	Less than one time in five	Less than half the time	About half the time	More than half the time	Almost always
1. Over the past month or so, how often have you had a sensation of not emptying your bladder completely after you finished urinating?	0	1	2	3	4	5
2. Over the past month or so, how often have you had to urinate again, less than two hours after you finished urinating?	0	1	2	3	4	5
3. Over the past month or so, how often have you found you stopped and started again several times when you urinated?	0	1	2	3	4	5
4. How often do you find it difficult to postpone urination?	0	1	2	3	4	5
5. Over the past month or so, how often have you had a weak urinary stream?	0	1	2	3	4	5
6. Over the past month or so, how often have you had to push or strain to begin urination?	0	1	2	3	4	5
	Not at all	Once every 8 hours	Once every 4 hours	Once every 3 hours	Once every 2 hours	At least once every hour
7. Over the past month or so, how often did you most typically get up at night to urinate?	0	1	2	3	4	5

**Total per column**      \_\_\_\_\_

\_\_\_\_\_  
Patient Name

\_\_\_\_\_  
Patient Signature

\_\_\_\_\_  
Date This Form was Completed

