**URINARY FUNCTION**

This section is about your urinary habits. Please consider **ONLY THE LAST 4 WEEKS**.

1. Over the **past 4 weeks**, how often have you leaked urine?

- More than once a day..... 1
- About once a day..... 2
- More than once a week..... 3 (Circle one number)
- About once a week..... 4
- Rarely or never..... 5

2. Over the **past 4 weeks**, how often have you urinated blood?

- More than once a day..... 1

- About once a day..... 2
- More than once a week..... 3 (Circle one number)
- About once a week..... 4
- Rarely or never..... 5

3. Over the **past 4 weeks**, how often have you had pain or burning with urination?

- More than once a day..... 1
- About once a day..... 2
- More than once a week..... 3 (Circle one number)
- About once a week..... 4
- Rarely or never..... 5

4. Which of the following best describes your urinary control **during the last 4 weeks**?

- No urinary control whatsoever..... 1
- Frequent dribbling..... 2 (Circle one number)
- Occasional dribbling..... 3
- Total control..... 4

5. How many pads or adult diapers per day did you usually use to control leakage **during the last 4 weeks**?

- None..... 0
- 1 pad per day..... 1
- 2 pads per day..... 2 (Circle one number)
- 3 or more pads per day..... 3

6. How big a problem, if any, has each of the following been for you **during the last 4 weeks**?  
(Circle one number on each line)

	No Problem	Very Small Problem	Small Problem	Moderate Problem	Big Problem
a. Dripping or leaking urine .....	0	1	2	3	4
b. Pain or burning on urination.....	0	1	2	3	4
c. Bleeding with urination.....	0	1	2	3	4
d. Weak urine stream or incomplete emptying.....	0	1	2	3	4

e. Waking up to urinate.....	0	1	2	3	4
f. Need to urinate frequently during the day .....	0	1	2	3	4

7. Overall, how big a problem has your urinary function been for you **during the last 4 weeks?**

- No problem..... 1
- Very small problem..... 2
- Small problem..... 3 (Circle one number)
- Moderate problem..... 4
- Big problem..... 5

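### Acute toxicity is a stated objective, but no toxicity assessment is scheduled until 6 weeks after treatment, so transient non-serious acute events may be under-counted

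*Combined protocol and SAP*

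**What the plan says.** The objective in section 2.0 is to evaluate the "local control rate as well as acute and late toxicity rates" of SBRT. Section 2.2.3 lists acute and late toxicities among the data to be collected, and hypothesis 2.1.1 is that complication rates will be acceptable. The endpoints are narrower. In section 2.3.2, "Secondary endpoint will be late toxicity rate", and acute complications appear only in a bullet about grading.

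Section 10.1 describes its table as "suggested patient follow-up intervals and evaluations that may be performed to either assess for treatment toxicity or tumor response to SBRT". The columns run from Pre-Rx straight to 6 weeks after treatment, then 3, 6 and 9 months and 1 year. The Toxicity Assessment row is blank at Pre-Rx and first marked at 6 weeks. AUA/EPIC is marked at Pre-Rx and next at 6 weeks.

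EPIC (Appendix V) tells the patient to consider "ONLY THE LAST 4 WEEKS". Six of the seven AUA items (Appendix IV) are framed like this one: "Over the past month or so, how often have you had a weak urinary stream".

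Under section 10.3.2 all serious adverse events are recorded when they occur and adverse events are graded by CTC, but no collection period is set for non-serious events. Section 8.2 (treatment delivery) and the Treatment Form (Appendix VII) contain no toxicity item. The Follow-up Visit Form (Appendix VIII) has an acute block with grade, timing, treatment and comments columns.

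**The concern.** The acute events that section 10.3 tells investigators to expect are largely symptoms: dysuria, frequency, loose stools, rectal irritation, dermatitis, malaise. Many can arise during a short course or just after it and settle within weeks. A site that follows the table exactly would not grade them at the time. It would first ask at 6 weeks, with questionnaires whose recall does not reach that far back.

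At stake is the acute half of the section 2.0 objective, and the complication part of hypothesis 2.1.1. If short-lived events are missed, the error favours that hypothesis. Because the schedule is only suggested, some patients may be assessed earlier than others, so ascertainment could also vary within the trial.

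**Working it through.** The plan gives no figure on this point to reproduce. The check is calendar arithmetic.

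**Inputs**
- First scheduled toxicity assessment: 6 weeks = day 42 (section 10.1), read as counted from the last SBRT fraction.
- Recall R: 28 days for EPIC; 28-31 days for AUA, taking a month or so as up to 31 days.
- Monotherapy course: 4-5 fractions at 2 to 3 per week (section 7.2.1). I assume Monday/Wednesday/Friday or Monday/Thursday delivery and count both end days.

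**Reach of the questionnaires at the 6-week visit.** Earliest day covered = 42 − R.
- EPIC: 42 − 28 = day 14.
- AUA: 42 − 31 = day 11, to 42 − 28 = day 14.

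**Time not covered.** With C the course length in days, uncovered days = C + (42 − R), out of C + 42.

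| Fractions | Per week | C | Uncovered, R = 31 | Uncovered, R = 28 | First fraction to visit | Share uncovered |
|---|---|---|---|---|---|---|
| 4 | 3 | 8 | 19 | 22 | 50 | 38-44% |
| 4 | 2 | 11-12 | 22-23 | 25-26 | 53-54 | 42-48% |
| 5 | 3 | 10-11 | 21-22 | 24-25 | 52-53 | 40-47% |
| 5 | 2 | 15 | 26 | 29 | 57 | 46-51% |

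So 19-29 of the 50-57 days lie outside both recall windows, between 19/50 = 38% and 29/57 = 51%. These days comprise the whole SBRT course and the first 11-14 days after it.

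**Men given pelvic radiotherapy first.** The course is 25 fractions. At an assumed 5 per week it spans 33 days. Allow an assumed 0-14 day gap and 3-8 days for a 2-3 fraction boost:
- shortest: 33 + 0 + 3 + 42 = 78 days (11.1 weeks);
- longest: 33 + 14 + 8 + 42 = 97 days (13.9 weeks).

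If both courses are given on study, the first scheduled toxicity assessment comes about 11-14 weeks after the first pelvic fraction, with none between the two courses.

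**Size of any under-count.** Observed rate = true rate × (1 − share of events missed). The documents give no value for the share missed, so the effect on the rate cannot be computed.

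**The case against.** The strongest reply is that no named endpoint or planned analysis is touched. Biochemical control is primary and late toxicity is secondary. Section 11.5 plans only overall survival, biochemical control and the incidence of serious adverse events, and serious events are recorded whenever they occur. This stands and limits the point to non-serious acute events, which are mostly grade 1-2. It does not remove acute toxicity from section 2.0 or from the data list in 2.2.3.

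A second reply is that the 4-week limit belongs to the questionnaires. The clinician's CTCAE assessment has no recall limit, the Timing column lets an earlier event be entered, and nothing bars a site from assessing sooner. This also stands. A reader might infer that events during treatment go unrecorded or will certainly be under-counted. The documents support only that they depend on recall or chart notes and may be.

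Three further readings go beyond the documents.
- A reader might apply an assumed loss to a cited acute rate. The grade 2 rates in the Introduction run from under 5% to 42%, and nothing says what share would resolve unreported by week 6.
- A reader might infer that comparison with the cited series would be flattering. The documents do not say when those series assessed acute toxicity.
- A reader might extend the point to complications of fiducial placement. The objective concerns toxicity of SBRT, and the form's adverse event table is for radiation-related events.

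Finally, sections 3.1.5 and 3.2.5 admit men whose pelvic radiotherapy was part of combination therapy. That course may precede registration, and the meaning of Pre-Rx for these men is not defined. The fix must allow for this.

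**Conclusion.** The point holds in limited form. The plan commits to an acute toxicity rate but schedules no toxicity assessment before day 42 and no baseline grade. For monotherapy the questionnaires leave 38-51% of the interval from first fraction to first visit uncovered, given that Post-Rx is counted from the last fraction and given the delivery patterns and recall lengths assumed above. Non-serious acute events that resolve before week 6 may be under-counted, in the direction that favours hypothesis 2.1.1. That direction is an inference about transient symptoms, and its size is unknown. The blank at Pre-Rx is a related weakness that can work the other way, since symptoms present before treatment may be graded as toxicity. The named endpoints and the serious-event analysis are unaffected. This is a worthwhile, inexpensive improvement and does not threaten the trial's main result.

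**What to change.** In the section 10.1 table:
- Add a CTCAE toxicity assessment at Pre-Rx, to give a baseline grade, and one at the last SBRT fraction. Use the acute block of the existing Follow-up Visit Form for both.
- For men who receive the 45 Gy pelvic course on study, add one at the end of that course. For men whose pelvic course preceded registration, use the Pre-Rx assessment, made before SBRT.
- At the 6-week visit, record the worst CTCAE grade since the last fraction and its timing, with chart review. Days 0-14, which no questionnaire reaches, are then asked about explicitly. They still rest on recall and the chart, but in the same way for every patient.
- Report the acute rate as the worst grade across these post-baseline assessments, read against the baseline grade.

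The cost is one extra copy of an existing form at each added assessment, at visits patients already attend, plus a short chart review at 6 weeks. Only measurement changes. The downside for the sponsor is that the reported acute toxicity rate may be higher.

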The results of a phase I dose escalation trial conducted by the University of Texas Southwestern Medical Center were presented at the American Society of Clinical Oncology 2010 Genitourinary Cancers Symposium. Forty-five patients with low to intermediate risk prostate cancer were treated with a 5 fraction SBRT regimen using image guidance, intensity modulation, and a rectal balloon with pretreatment enema. The starting radiation dose was 45 Gy in 5 fractions with subsequent dose escalation to 47.5 Gy and 50 Gy. Patients were followed for toxicity using CTCAE (Common Terminology Criteria for Adverse Events) v3 scoring, as well as AUA (American Urological Association) and EPIC questionnaires. After a median follow-up of 12 months, the investigators observed no grade 3 gastrointestinal toxicities and only one patient with grade 3 genitourinary toxicity. Mean AUA score before SBRT was 5 and during follow-up increased to 8-9. EPIC rectal mean scores were decreased at 6 weeks to 12 months but returned to baseline at 18 months. PSA control was 95% using the nadir-plus-2 definition and 100% using the 3-consecutive-rises definition. Currently, the phase II study that is being conducted utilizes 50 Gy in 5 fractions. (15)

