## **10.3 Toxicity**

**10.3.1** The patient will fill out the American Urological Association (AUA) Symptom Score Sheet and Expanded Prostate Cancer Index Composite (EPIC) questionnaire for gastrointestinal, urinary and sexual quality of life. (14) (Appendix IV and Appendix V, respectively)

**10.3.2** The investigator will report and record all serious adverse events that occur. Adverse events should be reported using the CTC grading system (Appendix III).

**10.3.2** Examples of anticipated acute adverse events include:

- General malaise
- Urinary irritative or obstructive symptoms – dysuria, increased urinary frequency, nocturia, weak stream, hesitancy, and possible urinary retention
- Rectal irritation – loose stools, cramping, straining, hemorrhoidal inflammation
- Radiation dermatitis – dryness, tanning, redness, itching
- Localized hair loss
- Musculoskeletal pain

**10.3.3** Examples of anticipated late adverse events include:

- Bleeding, ulceration and/or perforation of the bladder, rectum, or small bowel
- Neurologic changes including motor weakness, numbness, paresthesias, and/or bowel or bladder dysfunction
- Persistent changes in bowel or bladder habits
- Small bowel obstruction
- Urethral stricture resulting in urinary retention
- Localized skin fibrosis, edema, and/or ulceration
- Erectile dysfunction
- Radiation-induced secondary malignancy

**10.3.4** Reporting of unanticipated or serious adverse events will be reported according to the institutions IRB policy. An unanticipated adverse event is defined as follows:

Any serious adverse effect on health or safety or any life-threatening problem or death caused by, or associated with, stereotactic body radiotherapy, if that effect, problem, or death was not previously identified in nature, severity, or degree of incidence in the investigational plan or application (including a supplementary plan or application), or

any other unanticipated serious problem associated with a treatment that relates to the rights, safety, or welfare of subjects.

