13.3 Appendix III

**Common Terminology Criteria for Adverse Events v3.0 (CTCAE)**

	GRADE				
Toxicity	1	2	3	4	5
CONSTITUTIONAL					
Fatigue	Mild fatigue over baseline	Moderate or causing difficulty performing some ADL	Severe fatigue interfering with ADL	Disabling	-
Fever	100.4-102.2°F	102.3-104.0°F	> 104.0°F for < 24 hr	> 104.0°F for > 24 hr	Death
Weight loss	5 - < 10% of baseline	10 - < 20% of baseline	≥ 20% of baseline; tube feeding or TPN indicated	-	-
PAIN					
Pain due to radiation	Mild pain not interfering with function	Moderate pain: pain or analgesics interfering with function, but not interfering with ADL	Severe pain: pain or analgesics severely interfering with ADL	Disabling	-
Myositis (inflammation or damage of muscle)	Mild pain not interfering with function	Pain interfering with function, but not interfering with ADL	Pain interfering with ADL	Disabling	Death
SKIN					
Radiation dermatitis	Faint erythema or dry desquamation	Moderate to brisk erythema; patchy moist desquamation, mostly confined to skin folds and creases; moderate edema	Moist desquamation other than skin folds and creases; bleeding induced by minor trauma or abrasion	Skin necrosis or ulceration of full thickness dermis; spontaneous bleeding from involved site	
Telangiectasia	Few	Moderate number	Many and confluent	-	-
Ulceration	-	Superficial ulceration < 2 cm size; local wound care; medical intervention indicated	Ulceration ≥ 2 cm size; operative debridement, primary closure or other invasive intervention indicated (ex. Hyperbaric oxygen)	Life-threatening consequences; major invasive intervention (ex. Complete resection, tissue reconstruction, flap, grafting)	Death
Fibrosis	Increased density, "spongy" feel	Increased density with firmness or tethering	Increased density with fixation of tissue; operative intervention indicated; interfering with ADL	Life-threatening; disability; loss of limb; interfering with vital organ function	Death
Soft Tissue Necrosis	-	Local wound care; medical intervention indicated	Operative debridement or other invasive intervention indicated (ex. Hyperbaric oxygen)	Life-threatening consequences; major invasive intervention indicated (ex. Tissue reconstruction, flap, or grafting)	Death
NEUROLOGY					

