Neuropathy: Motor	Asymptomatic, weakness on exam/testing only	Symptomatic weakness interfering with function, but not interfering with ADL	Weakness interfering with ADL; bracing or assistance to walk (e.g. cane or walker) indicated	Life-threatening; disabling (e.g. paralysis)	Death
Neuropathy: Sensory	Asymptomatic, lost deep tendon reflexes or paresthesia (including tingling), not interfering with function	Symptomatic alteration or paresthesia (including tingling), interfering with function, not interfering with ADL	Sensory alteration or paresthesia interfering with ADL	Disabling	Death

GI TRACT					
Nausea	Loss of appetite without alteration in eating habits	Oral intake decreased without significant weight loss, dehydration, or malnutrition; IV fluids indicated < 24 hr	Inadequate oral caloric or fluid intake; IV fluids, tube feedings, or TPN indicated $\geq$ 24 hr	Life-threatening consequences	Death
Vomiting	1 episode in 24 hr	2-5 episodes in 24 hr; IV fluids indicated < 24 hr	$\geq$ 6 episodes in 24 hr; IV fluids or TPN indicated $\geq$ 24 hr	Life-threatening consequences	Death
Diarrhea	Increase of < 4 stools per day over baseline; mild increase in ostomy output compared to baseline	Increase of 4-6 stools per day over baseline; IV fluids indicated < 24 hrs; moderate increase in ostomy output compared to baseline; not interfering with ADL	Increase of $\geq$ 7 stools per day over baseline; IV fluids indicated $\geq$ 24 hrs; hospitalization; severe increase in ostomy output compared to baseline; interfering with ADL	Life-threatening consequences (e.g., hemodynamic collapse)	Death
Enteritis	Asymptomatic, pathologic or radiographic findings only	Abdominal pain; mucous or blood in stool	Abdominal pain, fever, change in bowel habits with ileus; peritoneal signs	Life-threatening consequences (ex. Perforation, bleeding, ischemia, necrosis)	Death
Ulceration	Asymptomatic, radiographic or endoscopic findings only	Symptomatic; altered GI function (altered dietary habits, oral supplements); IV fluids indicated < 24 hr	Symptomatic and severely altered GI function (inadequate oral caloric or fluid intake); IV fluids, tube feedings, or TPN indicated $>$ 24 hr	Life-threatening consequences	Death

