Urinary frequency/urgency	Increase in frequency or nocturia up to 2 x normal; enuresis	Increase >2 x normal but <hourly	≥1 x/hr; urgency; catheter indicated	-	-
Urinary retention	Hesitancy or dribbling, no significant residual urine; retention occurring during the immediate postoperative period	Hesitancy requiring medication; or operative bladder atony requiring indwelling catheter beyond immediate postoperative period but for <6 weeks	More than daily catheterization indicated; urological intervention indicated (e.g., TURP, suprapubic tube, urethrotomy)	Life-threatening consequences; organ failure (e.g., bladder rupture); operative intervention requiring organ resection indicated	Death
Stricture, GU	Asymptomatic, radiographic or endoscopic findings only	Symptomatic but no hydronephrosis, sepsis or renal dysfunction; dilation or endoscopic repair or stent placement indicated	Symptomatic and altered organ function (e.g., sepsis or hydronephrosis, or renal dysfunction); operative intervention indicated	Life-threatening consequences; organ failure or operative intervention requiring organ resection indicated	Death
MUSCULOSKELETAL					
Fracture	Asymptomatic, radiographic findings only	Symptomatic but non-displaced; immobilization indicated	Symptomatic and displaced; operative intervention indicated	Disabling	Death
METABOLIC					
Albumin	3-4 g/dL	2-2.99 g/dL	< 2 g/dL		Death
Alkaline phosphatase	> nl – 2.5 x nl	> 2.5 – 5 x nl	> 5 – 20 x nl	> 20 x nl	-
ALT	> nl – 2.5 x nl	> 2.5 – 5 x nl	> 5 – 20 x nl	> 20 x nl	-
AST	> nl – 2.5 x nl	> 2.5 – 5 x nl	> 5 – 20 x nl	> 20 x nl	-
Bilirubin	> nl – 1.5 x nl	> 1.5 – 3 x nl	> 3 – 10 x nl	> 10 x nl	-
Creatinine	> nl – 1.5 x nl	> 1.5 – 3 x nl	> 3 – 6 x nl	> 6 x nl	Death
SECONDARY MALIGNANCY	-	-	Non-life-threatening basal or squamous cell carcinoma of the skin	Solid tumor, leukemia, or lymphoma	Death

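### No CTCAE grade is taken before treatment and no rule covers pre-existing symptoms, so prior symptoms may be counted or misgraded as treatment toxicity

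*Combined protocol and SAP*

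**What the plan says.** Section 10.1 (Study Parameters) introduces its table with "The following are suggested patient follow-up intervals and evaluations that may be performed". The row "Toxicity Assessment" has no mark before treatment. It is marked at 6 weeks, 3, 6 and 9 months, and at 1 year at the radiation oncologist's discretion. The rows for history, examination and weight, for disease status, for PSA and for "AUA/EPIC Questionnaire" are all marked before treatment.

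Appendix III (CTCAE v3.0) defines some grades as change. Fatigue grade 1 is "Mild fatigue over baseline", diarrhea grade 1 begins "Increase of < 4 stools per day over baseline", and urinary frequency/urgency grade 1 is "Increase in frequency or nocturia up to 2 x normal; enuresis". Other terms, such as urinary retention, incontinence, GU stricture, GI bleeding and neuropathy, are graded on what is present at the visit, with no reference to an earlier state.

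Section 10.3.1 has patients complete the AUA score and the EPIC "questionnaire for gastrointestinal, urinary and sexual quality of life". The follow-up form in Appendix VIII heads its adverse-event table as events related to radiation therapy, with separate acute and late lists. Section 2.0 names acute and late toxicity rates as objectives, section 2.3.2 makes late toxicity the secondary endpoint, and section 2.1.1 hypothesises acceptable complication rates. The only safety analysis in section 11.5 is the incidence of serious adverse events.

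**The concern.** With no control arm, each man's own pre-treatment state is the only internal comparison for toxicity. Symptomatic men can enter: section 3 admits Zubrod 0 to 3 and prostates up to 100 cc, and excludes nobody for urinary or bowel symptoms. The protocol's own background shows that symptoms before treatment are to be expected. Of a cited phase I SBRT study it says "Mean AUA score before SBRT was 5 and during follow-up increased to 8-9".

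If the baseline grade is not taken and no counting rule is set, two investigators could record the same patient differently, and the reported rate would mix old and new problems in unknown proportion. A CTCAE grade not taken before treatment cannot be reliably reconstructed later.

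**Working it through.** The plan states no target toxicity rate, threshold or sample size, so there is no figure to reproduce. The check has three steps.

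**1. Which terms need a baseline, and is one scheduled?**

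| Definition in Appendix III | Terms | Place on the Appendix VIII form | Effect of having no baseline grade |
|---|---|---|---|
| Relative to baseline, reference measured | Weight loss (grades 1–3) | Acute list | None; weight is scheduled before treatment |
| Relative to baseline or normal, reference only approximate | Fatigue (grade 1), diarrhea (grades 1–3), urinary frequency (grades 1–2) | Acute list | Grade imprecise |
| Absolute | GU stricture, GI bleeding | Late list | A prior problem can score directly |
| Absolute | Neuropathy | Both lists | As above |
| Absolute | Urinary retention, incontinence | No line of their own | As above, if recorded |
| Not graded | Impotence | Late list | A prior problem can be ticked; EPIC is the only baseline |

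**2. Can the questionnaires supply the reference value?** Only roughly. EPIC item 13 bands daily bowel movements as two or less, three to four, or five or more. Take a man in the middle band who has 7 stools a day at follow-up (an illustrative count). If his baseline was 3, the increase is 7 − 3 = 4, which is diarrhea grade 2. If it was 4, the increase is 7 − 4 = 3, which is grade 1. The same baseline answer fits both grades. No section maps AUA or EPIC answers to CTCAE grades.

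**3. How large could the excess be?** Let *t* be the true rate of new toxicity and *b* the proportion of men with a qualifying symptom before treatment. If the two are independent and every prior symptom persists and is counted, then

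apparent rate = 1 − (1 − *b*)(1 − *t*).

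The values of *t* are the late grade II urinary rates quoted in section 1.0: 2% (35 Gy level) and 5.8% (36.25 Gy level) in the series using rectal amifostine, and 24% in the earlier series compared with it. The values of *b* are assumptions; the documents give none. For example, with *b* = 10% and *t* = 5.8%, 1 − 0.90 × 0.942 = 0.152. With *b* = 30%, 1 − 0.70 × 0.942 = 0.341.

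| *b* (assumed) | *t* = 2% | *t* = 5.8% | *t* = 24% |
|---|---|---|---|
| 0% | 2.0% | 5.8% | 24.0% |
| 5% | 6.9% | 10.5% | 27.8% |
| 10% | 11.8% | 15.2% | 31.6% |
| 20% | 21.6% | 24.6% | 39.2% |
| 30% | 31.4% | 34.1% | 46.8% |

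If only a fraction *c* of prior symptoms is counted, replace *b* by *c* × *b*. With *b* = 20% and *c* = one half, the 10% row applies. With *c* = 0 the excess is zero.

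The cited AUA means do not fix *b*. They imply that 5/9 = 56% to 5/8 = 63% of the mean follow-up score was already there before treatment, but this is a share of a mean score. It is not a prevalence of any CTCAE grade.

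**The case against.** The strongest reply is that the plan already has a baseline and an attribution step. Before treatment it schedules history, examination, weight, AUA and EPIC. The questionnaires cover nocturia, urgency, leakage, pads, dysuria, hematuria, bowel symptoms, erections and energy, and are repeated at each scheduled visit. The form asks only for events related to radiation therapy, and section 10.3 describes the late bowel and bladder events as changes. Much of this stands, and it rules out four stronger readings that a reader might infer:

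- *That pre-existing symptoms are counted as toxicity.* No section says so. The form's heading points the other way, so the most that can be said is that they may be counted.
- *That old and new symptoms cannot be separated.* AUA and EPIC often show whether a urinary, bowel or sexual symptom was there before. What is missing is a CTCAE grade and a rule.
- *That grades defined against baseline are inflated.* With a known baseline, such grades exclude stable prior symptoms. Without one they become imprecise. Direct inflation is a risk for the absolute grades.
- *That the baseline-referenced terms distort the late-toxicity endpoint.* Fatigue, diarrhea and urinary frequency are on the form's acute list. The late rate is exposed through the absolute grades and impotence.

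What does not stand is that these safeguards suffice. The heading gives no criterion for attribution, and it does not separate SBRT from the 45 Gy pelvic course that some men receive first. The pre-treatment history in section 4 carries no symptom grading.

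A further objection is that a cited mean AUA of 5, on a form with a maximum of 7 × 5 = 35, is low. That is fair: it shows that symptoms exist before treatment, and nothing about how many men would reach grade 2.

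**Conclusion.** The concern holds in a limited form. The schedule takes no pre-treatment CTCAE grade, and no section in the text reviewed says how pre-existing symptoms are handled. Prior symptoms may therefore be counted or misgraded. Acute rates are affected through imprecise reference values for fatigue, diarrhea and urinary frequency. Acute and late rates are affected through absolutely graded terms, and the late rate also through impotence. Weight loss is not affected.

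The size is unknown. The range of 15% to 34% for a true 5.8% is a worst-case illustration. It rests on an assumed baseline prevalence of 10% to 30%, independence, persistence of every prior symptom and no attribution at all. With perfect attribution the excess is zero. Because the plan sets no threshold for acceptable complications, it cannot be said that any conclusion would reverse.

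Confidence is moderate. Appendix VI (the patient demographic form) is listed in the index but is not in the text available for review, so a baseline symptom field there cannot be excluded. The gap should be corrected, but it does not invalidate the study.

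**What to change.** 1. Mark the toxicity row at the pre-treatment visit in section 10.1. Because that table is only suggestive, also state in section 10.3 that the baseline grading is required.
2. At the existing pre-treatment history and examination, grade the clinical (non-laboratory) CTCAE terms in Appendix III, including those on the Appendix VIII form. Leave out albumin, liver enzymes, bilirubin and creatinine: before treatment these are taken only where clinically indicated, and requiring them would add blood tests.
3. For terms defined as change, record the reference value itself, such as stools per day and voiding frequency by day and night.
4. For impotence, which Appendix III does not grade, use the EPIC sexual items already collected at baseline.
5. Say whether, for men who receive pelvic radiotherapy first, the baseline is taken before that course or before SBRT.
6. In sections 2.3.2 and 11.5, define acute and late toxicity as the worst grade in the period that exceeds the patient's baseline grade, and report the crude worst grade beside it. The difference between the two then shows how much the baseline matters.

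The cost is one extra form at a visit that already takes place, with no new visit or test.
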